## 1.0 PROTOCOL

**Study Design Overview:** This is a Phase III Clinical Trial. Our overall goals are to evaluate the effectiveness of nonoperative and operative interventions in patients with adult symptomatic lumbar scoliosis (ASLS) and to identify important clinical and radiographic determinants of change in patient-reported HRQOL. To accomplish these goals, a 5-year cooperative, multi-center longitudinal randomized study with a concurrent observational cohort is proposed.

**Specific Aim #1:** Compare the outcomes of surgery and nonoperative treatment in patients aged 40 to 80 with ASLS defined as a lumbar curve with a coronal Cobb measurement of 30° or more, and either of the following: Oswestry Disability Index (ODI) score of 20 or more; or Scoliosis Research Society Quality of Life (SRS-QOL) instrument score of 4.0 or less, in the domains of pain, function and/or appearance.

Null Hypothesis: Nonoperative and operative treatment groups will have similar outcomes at follow-up.

**Specific Aim #2:** Evaluate the impact of patient factors (age, gender, socioeconomic status, education) and comorbidities [mental health, body mass index (BMI) and bone mineral density (BMD)] on adverse events and treatment outcomes for both the non-operative and operative arms. Incorporate these variables into a prediction model to help identify those patients most likely to benefit from either a surgical or non-operative approach.

Hypothesis: Age, gender, socioeconomic status, education, and comorbidities will have an impact on the final result at 2-4 years post-intervention.

From the adult section of the SDSG, we will utilize five centers that have consistently enrolled the most ASLS patients. From 2004 through 2006 these five centers enrolled 155 non-operative and 141 operative patients meeting the ASLS criteria. Each center has committed to the enrollment of at least 10 patients per year, and across all 5 sites we expect to average 20 patients per year, to reach a targeted enrollment of 300 patients over 3 years.

As summarized in the flow chart shown in Figure 1 eligible patients at each site will be informed about the study and will be able to participate in one of two ways. Those agreeing to randomization will be randomized to operative or non-operative care, while those willing to participate in the study but not accepting random treatment assignment will be followed in a prospective observational cohort. The primary outcome measure will be longitudinal change in disease-specific quality of life as measured by the Scoliosis Research Society-Quality of Life (SRS-QOL) subscore.

We plan to recruit a total of 300 patients into the trial. Based on our preliminary data, we expect 90% participation and about 30% randomization, resulting in a total of about 82 in the randomized trial and 188 in the observational cohort. While we will perform both intent-to-treat and as treated analysis, intent-to-treat analysis of the randomized trial will provide the most internally valid, un-confounded estimate of the effect of surgery, while the inclusion of the prospective observational cohort will help assess the external validity of the results and include a much broader spectrum of patients with ASLS than an RCT alone.

### 1.1 Eligible Participants:

This is a study of patients

[figure not shown]
- aged 40 to 80 years with
- ASLS defined as
  - lumbar curve with a coronal Cobb measurement  $\geq 30^\circ$ , and
  - **either of the following:**
    - Oswestry Disability Index (ODI) score  $\geq 20$  **or**
    - SRS-QOL score  $\leq 4.0$  in the domains of pain, function and/or appearance.
- **If assigned to surgical intervention** (by randomization or patient preference), the intervention plan would include, at a minimum, the Cobb levels of the Thoracolumbar/lumbar spine.

Patients 81 years or older are not eligible for inclusion, as most providers would not recommend major surgical procedures of this nature for these patients in this age group due to the increased risk of perioperative morbidity and mortality. Eligibility for participation is not restricted based on gender, ethnicity or principle language.

Excluded from participation are patients with any of the following factors:

- Substantial cardiac, pulmonary, renal or metabolic disease that, in the judgment of the surgical team, would preclude performing an operative procedure without undue risk of morbidity and mortality
- Concomitant high-grade spondylolisthesis (Grade  $\geq 3$ )
- Prior thoracic or multiple level lumbar laminectomy or decompression [single or two level lumbar decompression (e.g., herniated disc) will not be an exclusion]
- Prior thoracic or lumbar fusion
- Osteoporosis evidence by a dual-energy x-ray absorptiometry (DEXA) T-score  $<-3.0$  at the femoral neck for patients considered to be at risk (post-menopausal females, males  $\geq 60$  years of age, steroid dependent rheumatoid arthritis, status post organ transplantation, etc.). Patients may be randomized prior to obtaining DEXA results. Non-Surgical patients may initiate non-surgical treatments prior to completion of DEXA (if required) as non-surgical treatments will not affect DEXA results BUT DEXA must be completed and results entered within 3 months of enrollment. Surgical patient must have DEXA prior to surgical intervention. Waivers will be provided for patients meeting inclusion criteria who have had bilateral total hip replacements only if t score of spine and wrist are provided.
- Neuromuscular scoliosis (e.g., spinal muscular atrophy, cerebral palsy, Parkinson's Disease, post-polio syndrome, Charcot Marie Tooth disease)
- Congenital scoliosis in the lumbar spine. Congenital anomalies of the cervical or thoracic spine are acceptable.
- Spine tumor, infection or connective tissue disorder
- Cognitively impaired or unable/unwilling to comply with follow-up
- Pregnancy or planning on conceiving during time of study involvement
- Ankylosing Spondylitis
- Past history of vertebroplasty or kyphoplasty of the thoracic or lumbar spine

Figure 1: Patient flow and Triage

**1.2 Identification and Enrollment:** Site investigators and/or research coordinators will identify potential study participants based on patient history, physical exam, radiographs and HRQOL scores. See Section 19 Administrative Forms: Screening Checklist. Patients meeting inclusion/exclusion criteria will be offered study participation. Potential patients will view a short video regarding study participation.

Eligible patients not consenting to study participation will be entered into the electronic database in a de-identified manner. Age, gender, inclusion criteria and reason for declining participation will be documented.

**1.3 Randomization and Observational Cohort Assignments:** Patients consenting to randomization will be randomized 1:1 to the non-operative or operative intervention arms. A permuted randomized block approach with blocks of size 4, 6 and 8 and stratified by site, age group (2 levels: 40-59 years of age, 60-80 years of age), gender and Cobb angle-based severity (2 levels: 30-54°, 55-100°) will be used to ensure representative treatment assignment across these demographic and disease-specific categories with approximately balanced assignment totals at interim intervals as well. Based on preliminary data, we anticipate that 57% of participants will be in the younger age category and 43% in the older age category.

Patient loss to follow-up can affect the randomization balance and quality. When a patient is lost to follow-up prior to treatment or because of an administrative error, such as qualifying a patient for inclusion in

the study when, in fact, study inclusion criteria were not met or exclusion criteria were initially missed, these patients will be removed from the study along with all study data. The guidelines for removing a patient from the study will follow the ICH guidelines; subjects who fail to satisfy an entry criterion will be excluded from the analysis under the following circumstances:

1. the entry criterion was measured prior to randomization;
2. the detection of the relevant eligibility violations can be made completely objectively;
3. all subjects receive equal scrutiny for eligibility violations; and
4. all detected violations of the particular entry criterion are excluded.

The study management plan is explicitly designed to minimize these events. Specifically, there will be electronic registration by site coordinator with explicit inclusion and exclusion criteria assessment on the enrollment form and review of registration by the Project Manager (PM) at Washington University.

In the observational cohort, the choice of nonoperative vs. operative care will be made by the patient guided by the provider's recommendation and presentation of existing data regarding nonoperative and operative care based on the following parameters: Patients with clinical symptoms of pain and functional limitations that are well controlled with non-operative care will be encouraged to pursue nonoperative care. Patients who have not demonstrated access or utilization to previous nonoperative care for their symptoms will be directed to non-operative care as an initial treatment. Enrollments into the observational arms will be closed when each arm's sample size is reached in order to achieve equal numbers of patients in each arm at the conclusion of the study.

**1.4 Study Interventions:** Regardless of study cohort participation (randomized or observational), interventions will not be implemented until the PM has confirmed appropriate enrollment. Nonoperative interventions will then be implemented as soon as possible. Due to the length and complexity of spinal deformity procedures, available dates for elective operative procedures may range from 1 to 6 months. Therefore, operative intervention will take place within six months of treatment assignment but baseline assessments, specifically MD assessment, patient reported HRQOL and treadmill tests must be completed within 6 months prior to intervention. Standardized protocol guidelines for nonoperative and operative treatment, as detailed below, will be followed by all sites.

**1.4.1 Non-operative Techniques:** To standardize non-operative treatments, sites will utilize one physician from their center with experience and expertise in non-operative management of spinal conditions (physiatrist, rheumatologist, or internist). For patients who live far from the enrolling center, referral to a local physiatrist will be made with a letter of introduction and a review of the proposed treatment plan from the study physician. A copy of the non-operative guidelines will be provided to all supervising nonoperative physicians.

The strategy for non-operative care for all non-operative patients will include:

1. **Physical Therapy:** Physical therapy will consist of treatment guided by one or a combination of: core stabilization, resistance training, directional preference, movement based, manual therapy, treatment-based group classification, aquatic therapy. Modalities will consist of strengthening arms and legs, improving aerobic conditioning, improving strength of spinal extensor muscles and teaching patients to avoid maneuvers that axially load or flex the lumbar spine. Physical therapy will include a combination of the following: water aerobics and/or reasonable forms of aerobic conditions. Strengthening of spinal extensor muscles will include upper and lower extremity muscles and avoidance of axial loading and flexion of the lumbar spine. Modalities for spine pain will include ultrasound, massage and transcutaneous electrical nerve stimulation (TENS) units.
2. **Injection Therapies:** Injections including epidural steroid and selective nerve root blocks will be used for patients with a significant component of radicular pain. Patients with back pain from facet joints will be offered facet blocks and medial branch ablation. This care pathway will be ordered by the enrolling physician, and enacted by a specialist in injection therapies. For leg pain, if a specific lumbar nerve root appears to be involved, a selective nerve root injection will

be considered. If leg pain is diffuse and involves both lower extremities, an epidural steroid will be considered.

3. **Pain Management:** Medications including non-steroidal anti-inflammatory drugs (NSAIDs) and narcotic analgesics will be used as appropriate. Medications will be started with non-steroidal and/or mild narcotics and only increased if necessary.
4. **Complementary and Alternative Approaches:** Patients in this study may access alternative healthcare resources including massage, acupuncture, acupressure and behavioral programs in an effort to improve pain and function. Alternative modalities will be made available to patients on a referral basis and the use of these modalities will be recorded for all patients. Weight loss will be strongly encouraged for body mass index (BMI) >27.

At each follow-up visit, patients will document the extent to which they have utilized these 4 modalities.

**1.4.2 Operative Techniques:** Operative treatments have been standardized across all study centers. Each center and surgeon will follow these guidelines. Therefore, surgical interventions should be completed at the study center so the kinds of operative treatment the patients receive will be relatively uniform from center to center and from surgeon to surgeon.

1. Extent of fusion: All spinal reconstruction cases will include at a minimum the Cobb levels of the curve. Additionally, the surgical reconstruction should include a balanced (neutral in rotation and stable, meaning centered on the center sacral line) vertebral segment at each end. All degenerative, rotated or listhetic segments will be included in the reconstruction.
2. Anterior release and inter-body grafting of the lumbar and thoracolumbar curves may be considered when the curve is rigid (i.e., does not reduce by 50% on push, side bending films, or supine films).
3. Pedicle subtraction and Smith-Petersen osteotomy can be performed as an alternate to anterior release for coronal or sagittal correction in rigid deformities.
4. All symptomatic spinal cord or nerve root compression will be addressed surgically with decompression.
5. Iliac bone graft and/or local bone will be used for fusion. This may be supplemented with bone growth factors and allograft.
6. Segmental instrumentation (pedicle screw, hook, and rod) will be utilized for all reconstructions. A universal goal will be to achieve at least 1.5 fixation points per level and dual fixation points at the top and bottom of the construct. Only rigid instrumentation systems will be implanted. No Dynamic Stabilization Devices will be used. No artificial disc replacements will be used in the lumbar spine.
7. Anterior structural support will frequently/usually be considered at L4-L5 and L5-S1, either as an anterior lumbar inter-body fusion (ALIF), posterior lumbar inter-body fusion (PLIF) or transforaminal lumbar inter-body fusion (TLIF) approach in patients being fused to the sacrum.
8. With fusion to the sacrum, 4-point sacropelvic fixation will be utilized in all circumstances, either in the form of four sacral screws or two sacral screws and two iliac screws.
9. Decompression/laminectomies will be warranted for segments with substantial spinal stenosis, both centrally and in the lateral recesses and in some cases in the foramen, when those stenotic segments are judged to be substantially stenotic and contributing to the patient's symptoms.
10. Surgeon judgment will be trusted on the fractional curve below. Most lumbar scoliosis consists of a curve that more or less goes from T10 to L3 or L4 with another curve that goes the other way between L3 or L4 and the sacrum. It will be expected that in most cases both these curves will be addressed and fused and instrumented. There may be some exceptions. There may be some cases in which the fractional curve is not included and there may be some cases in which the main curve is not included and only the fractional curve is included. If both curves are not

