## Adult Symptomatic Lumbar Scoliosis (ASLS) NIH R01 AR055176-01A2

---

included, it would be helpful for the surgical team to give a description of why the decision was made to include only one of the two curves.

If a consented patient is later not able to return to the original study center or a participating center for surgical intervention, *it is expected that the patient will continue in the study and participate as fully as possible.*

[figure not shown]
Surgical summary data will not be collected or posted to the database unless the surgery was performed by one of the participating investigators. If the surgery is not performed by a participating investigator, a Monitored Events report will be completed to reflect 1. SAE (Hospitalization) and if applicable, intervention cross over and 2. Discontinued treatment/Follow up continued.

All follow up data will be collected by mail and telephone contact. Sites will complete MD assessments by phone and follow up on any due diligence report reaching contact threshold. Sites should try to obtain copies of radiographic images annually.

Sites and patients will be reimbursed for 'long distance' follow up as outlined in the MOOP, Section 25.

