In the event that subjects do not return for a scheduled follow-up visit, or fail to return mailed questionnaires in a timely manner (within four weeks of mailing), site coordinators will contact subjects via telephone and/or e-mail. After two failed attempts, site coordinators will send a U.S. Postal Service certified letter to the subject's last known address. Address change service will be requested with all mailings. If certified mailings are returned undeliverable with no forwarding address, site coordinators will notify the PM, who will then conduct Internet searches and fee-based searches, such as ChoicePoint, to locate missing subjects.

Any patient deciding not to return to &/or continue treatment at the study will continue to be followed by mail and telephone, if the patient is willing. A monitored events report will be completed to document this change in patient and treatment status (Discontinued treatment/Follow up continued). Sites will mail QOLs to patients at interim and clinical follow up intervals. Site will follow up with patient if Due Diligence Report reaches contact threshold, to clarify any questionable patient information, &/or follow up on any questionnaires not returned. Site will ask patient to mail x-rays at annual milestones, as outlined in the protocol. Follow up MD assessments will only document treatments actually prescribed/recommended the Study PI (not MD from outside institutions).

**1.6 Project Manager (PM).** In addition to confirming appropriate participant study enrollment the PM will be responsible for tracking and monitoring productivity at all centers to further ensure complete and accurate data. It will be the responsibility of this individual to strive for 100% follow-up in both nonoperative and operative arms of the study.

The PM will have 24 hour/day access to the data collected and stored on study patients. The PM will query the database on a daily basis to monitor each site's productivity (enrollment and follow-up). Likewise, the sites will have access to the PM via alpha pager.

Responsibilities of PM:

- Develop an operations manual.
- Provide detailed training of site coordinators upon study initiation at start-up meetings and throughout the remainder of the study via conference calls and site visits. Conference calls with the PM and site coordinators will be held weekly until all sites are actively participating and comfortable with the study protocol, with decreasing frequency as study needs dictate.

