b. Variable Transformations: Transformations will be employed as needed to produce variables that conform to the distributional assumptions underlying the regression models that will be used. For example, some variables may be transformed to the logarithm scale for analysis, to reduce any marked positive skew; in these cases, results will be reported on the original scale of the variable to aid in interpretation.

Transformations may also be required to ensure additivity of variable effects in general linear models (for example, the outcome may be a quadratic rather than a linear function of age).

Stage 3 – Inferential Analysis:

Specific Aim 1: Compare the outcomes of surgery and non-operative treatment in patients aged 40 to 80 with ASLS defined as a lumbar curve with a coronal Cobb measurement $\geq 30^\circ$ and either of the following: Oswestry (ODI) score of 20 or more, or Scoliosis Research Society Quality of Life instrument (SRS-QOL) score of 4.0 or less in the domains of pain, function and/or appearance.

a. Primary Analyses: All the data analyses required to fulfill the specific aims of the study will be accomplished using statistical methods for repeated measures and longitudinal data using the SAS system's MIXED and GLIMMIX procedures for continuous and categorical outcomes, respectively. These procedures use maximum likelihood methods to estimate variances associated with the fixed and random effects of the model. In the randomized cohort, the primary analysis will be on an intent-to-treat basis. For the observational cohort, differences between treatment groups are expected at baseline and these will be controlled for by using covariate adjustment within the longitudinal regression models. We will model each HRQOL measure as the change at follow-up from baseline at each study month (i.e., at 3, 6, 12, 18, 24, 30, 36, 42, and 48 months), adjusting for baseline level while clustering the vector of outcomes within patients. Results will provide estimated means and standard deviations for the rate of change over the 12-month and 24-month (primary endpoint) follow-up periods, (1) assuming a linear rate of change, and (2) not assuming linearity. We will also report the 3-year and 3-year changes (and 95% confidence intervals) predicted by these models. For SRS-QOL and SF-12, component domains will be analyzed both combined and separately as described by Mangione et al.

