Addendum 8/29/12: (modified and edited 6/19/13) The primary analysis plan for this study is to first evaluate the RCT and OBS studies separately using mixed model longitudinal regression analysis using an intent-to-treat approach. As was done in the SPORT analysis, assessment Intervals are treated as a fixed effect, meaning with each interval developed based on the date of intervention. Data gathered prior to date of intervention (DOI) will be considered baseline and fixed data points gathered after DOI will be classified according the form designation (e.g., 3mo, 6mo). Data points gathered after DOI that were not fixed points (e.g., complications, severe adverse events) will be associated with a fixed interval based on the length of time from the data point and DOI. A second random effects variable (Delta) will be created within each interval that reflects the distance (no. of days) between the actual observed point and the center of the fixed interval that this point falls within. Thus, patients may have multiple data points within a fixed interval and the distance orTime of data collection relative to DOI within each fixed interval will be included in the model. In addition, a Delta random variable, defined as the distance between the center of the fixed interval and the Time of data collect will, also be created. The primary analysis will regress the change in outcome (eg for the pcs outcome d_pcs) on baseline pcs (b_pcs), treatment, interval, site and patient age and sex,

For the RCT cohort, the base model for PCS would be

$$d_{\text{pcs}} = b_{\text{pcs}} \text{ treatment} | \text{interval} | \text{time site age sex}$$

A secondary analysis will replace time with the Delta variable with the model forcing the Delta covariate to have a value of 0 – thereby adjusting the results to reflect the expected value for the outcome as if the outcome was assessed at the exact center of the fixed interval.

$$d_{\text{pcs}} = b_{\text{pcs}} \text{ treatment} | \text{interval} \text{ delta site age sex} \text{ delta / delta} = 0$$

Where:

T_DOI = Date dependent variable was collected – DOI WITH negative T_DOI values indicating outcomes being assessed prior to treatment and positive T_DOI values indicating the time after DOI that the outcome was evaluated. Note that T_DOI values are nested within d_pcs
= -pcs-b_pcs (a positive change would reflect improvement)

b_pcs = baseline pcs

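### Protocol 1.3 removes randomised patients lost before treatment, with all their data, which contradicts the intent-to-treat analysis; the effect on the estimate is small, but the randomised denominator and baseline data are lost

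*Protocol*

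**What the plan says.** Protocol 1.3 (Randomization and Observational Cohort Assignments) introduces the rule by noting that loss can harm the balance and quality of the randomisation, so the rule covers randomised patients. It has two triggers, "When a patient is lost to follow-up prior to treatment or because of an administrative error", and one consequence: "these patients will be removed from the study along with all study data". It then appeals to ICH guidance: "subjects who fail to satisfy an entry criterion will be excluded from the analysis under the following circumstances". Four conditions follow, all about eligibility violations.

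The SAP takes a different line. Under Stage 3, Specific Aim 1: "In the randomized cohort, the primary analysis will be on an intent-to-treat basis". The addendum of 8/29/12 analyses the RCT and the observational study "using mixed model longitudinal regression analysis using an intent-to-treat approach" and keeps the assigned treatment throughout. SAP 1.6.3 says that a patient's loss does not cancel the information given up to then. SAP Stage 1 plans to compare completers with dropouts.

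Two protocol passages limit whom the rule can reach. Section 1.4.2, on patients who cannot return to a participating centre for surgery, says "it is expected that the patient will continue in the study and participate as fully as possible". Section 1.5.3 says that patients who decide not to return "will continue to be followed by mail and telephone, if the patient is willing".

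**The concern.** Intent-to-treat needs every randomised patient to stay in the analysis set and be accounted for, whatever happens after assignment. Loss before treatment happens after assignment, so a rule that deletes these patients sets the randomised denominator by a post-randomisation event.

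The exposure also differs by arm. Protocol 1.4 says of surgery that "available dates for elective operative procedures may range from 1 to 6 months", while non-operative care is to begin promptly once enrolment is confirmed. The period in which a patient can count as lost before treatment is therefore longer in the operative arm.

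The data at stake exist. Protocol 1.5.2 has baseline data entered within a day of enrolment and before any intervention is activated. Removal takes those records out of three planned uses:
- the baseline comparison that judges whether randomisation worked (SAP 1.6);
- the completer and dropout comparison (SAP Stage 1);
- the choice of RCT covariates for their power to explain attrition (SAP 1.6.2 and the 8/29/12 addendum).

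**Working it through.** **Step 1. Do the ICH conditions cover loss before treatment?** Each is set against such a patient:

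| Condition in Protocol 1.3 | Patient lost before treatment |
|---|---|
| Criterion measured before randomisation | Not met: the loss comes after randomisation |
| Violation detectable fully objectively | No entry criterion has been violated |
| Equal scrutiny of all subjects for violations | Nothing to scrutinise; time at risk differs by arm |
| All detected violations of that criterion excluded | Does not apply |

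One exclusion criterion concerns being unable or unwilling to comply with follow-up. Later loss does not show a violation of it: the loss was not measured before randomisation and is not objective evidence of unwillingness at entry. The conditions support the administrative-error trigger only.

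**Step 2. Can the passages all be followed?** If the patient is removed with all data, the intent-to-treat set is not everyone randomised, information already given is cancelled, and the dropout comparison lacks its earliest dropouts. If the SAP is followed, the removal rule is not. They cannot all hold.

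**Step 3. Effect on the estimate.** The outcome is follow-up score minus baseline score, and follow-up visits are timed from intervention. A patient lost before treatment has no follow-up score and so gives the model no outcome record, kept or removed. Any power cost comes from the loss itself. The plan's sample sizes are untouched: a two-sample t-test at two-sided 0.05 and 80% power gives 37 per group at effect size 0.4/0.6 = 0.667 and 32 at 0.5/0.7 = 0.714, as in SAP Table 2.

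**Step 4. Size per patient.** The SAP reports 63 randomised. One patient is 1/63 = 1.6% of them, or 1/31.5 = 3.2% of one arm if the split is 1:1. The documents do not give the split or say whether 63 was counted before or after removals.

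**Step 5. What removal could mask (illustration).** The documents give no rate of loss before treatment, so these inputs are assumptions: arms of 32 (operative) and 31 (non-operative); 3 lost per arm after treatment starts, close to the 10% in SAP 1.6.3; k more lost before treatment, all in the operative arm; attrition computed from the data left after removal. Non-operative attrition is 3/31 = 9.7%.

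| k | Operative, all randomised: (3+k)/32 | Gap v 9.7% | Operative, after removal: 3/(32−k) | Gap v 9.7% |
|---|---|---|---|---|
| 1 | 4/32 = 12.5% | 2.8 points | 3/31 = 9.7% | 0.0 |
| 2 | 5/32 = 15.6% | 5.9 points | 3/30 = 10.0% | 0.3 |
| 3 | 6/32 = 18.8% | 9.1 points | 3/29 = 10.3% | 0.7 |

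At k = 0 there is nothing to mask.

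**The case against.** The strongest defence is that the rule is narrower than it looks. The sentence on ICH guidance follows at once and speaks only of entry criteria, and the preventive measures described next are all eligibility checks. Perhaps the four conditions were meant to govern every removal. That may be the intent, but loss before treatment is still named as a separate trigger, and a data manager following the text would remove the patient. The ambiguity is a reason to correct the wording.

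Three further points stand and limit the harm:
- With no follow-up score, these patients barely affect the treatment estimate.
- They need not vanish from view. The Project Manager keeps a participant list by site, cohort and arm (Protocol 1.6), and exits go on the Monitored Events form (1.5.1). Counts by arm could be rebuilt, so the masking in Step 5 arises only if attrition is computed from the reduced data. Baseline data are the firmer loss.
- Patients who decline surgery or stop attending but remain willing are still followed. A reader might infer that the rule strips out everyone assigned to surgery who does not have it; sections 1.4.2 and 1.5.3 do not support that.

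**Conclusion.** The rule is wrong as written. Protocol 1.3 tells the trial to delete a group of randomised patients whom the intent-to-treat analysis must keep, and its cited conditions do not justify this. The practical size is limited: little direct effect on the change-score estimate, and 1.6% of the randomised sample per patient removed. The real cost is the incomplete randomised denominator and the missing baseline data, possibly unequal by arm. How many patients are affected cannot be known from the documents.

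A reader might go further and infer that patients assigned to surgery who never have it fall out of the primary model, because Time is counted from the date of intervention and no such date is written for them, so that the treatment difference is overstated. The documents do not support that as a finding. SAP 1.6.3 and the addendum keep crossovers in their assigned group, the crossover section models surgery-to-non-operative patients explicitly, and intervals come from the form label. The Day 0 Non Operative Summary in the schedule is a plausible anchor, and the operations manual is not among these documents. What is missing is one clarifying sentence. Any figure for overstatement would need an assumed never-operated rate and total exclusion, against the plan's stated intent.

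**What to change.** In Protocol 1.3, strike loss before treatment as a trigger for removal. Limit removal to objective entry-criterion violations that meet all four listed conditions. State in the protocol and SAP that every other randomised patient, with baseline data, stays in the intent-to-treat set, the check on randomisation, the dropout comparison and the attrition accounting by arm. If any patients have already been removed for this reason, report the number by arm and restore their baseline records.

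As a minor clarification, state which date serves as the date of intervention for patients assigned to surgery who never have it, so that their scores enter the model as the SAP intends.

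The cost is wording: no new data and no change to visits. Reported attrition may be slightly higher, because early losses will now be counted.
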